March 25, 2022

At Baseline/Week 0, subjects will undergo clinical assessments (clinical SD Severity Score and IGA), review of concomitant medications, standardized clinical photography, and a Dermatology Life Quality index (DLQI) questionnaire (Appendix 2). Subsequent clinical assessments including standardized clinical photography, and questionnaire completion will be performed at follow up visits at Week 2, Week 4, and Week 6. Skin tape-strip samples will be collected for mechanistic studies (described below) at baseline (lesional and non-lesional facial skin), Week 2 (lesional facial skin), Week 4 (lesional facial skin), and Week 6 (lesional facial skin). Additional blood samples will be collected and stored at baseline and at Week 4 (or early termination, whichever is first) for potential future mechanistic analyses.

Control Subjects:

At Baseline/Week 0, subjects will undergo a review of concomitant medications, skin tape-strip samples will be collected for mechanistic studies (described below) of non-lesional facial skin, blood and urine sample collection for standard laboratory testing, and a blood sample for possible future mechanistic analyses.

MECHANISTIC ANALYSES:

We will characterize the molecular immune profiles of patients with SD at week 0 and week 4, with comparison to baseline profiles in healthy control subjects.

We plan to obtain lesional and non-lesional tape strip samples from facial skin of SD patients at week 0 and lesional facial skin samples at Week 4 (Primary Endpoint). Additionally, lesional facial skin samples will be collected at Week 2 and Week 6 and stored for potential future analysis. Blood samples at baseline and at Week 4 will be collected and stored for potential future analysis.

Gene expression studies on tape strip samples will be performed using Illumina NovaSeq 6000 for RNA-seq, and proteomic studies on tape strip samples will be performed using the Olink Explore panel, which includes >1,500 protein analytes.

PATIENT POPULATION:

Prior to enrollment, all subjects must meet the following inclusion and exclusion criteria:

Inclusion Criteria For SD Subjects:

- 1) Male or female subjects \geq 18 years of age at the time of signing the informed consent document.
- 2) Subject is able to understand and voluntarily sign an informed consent document prior to participation in any study assessments or procedures.

- 3) Subject is able to adhere to the study visit schedule and other protocol requirements.

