- Review personal and family history of SD and other inflammatory skin diseases
- Record all concomitant medications as well as all those received within 30 days prior to screening
- Record all prior therapies for SD
- Urine pregnancy test for all female subjects of child-bearing potential
- SD Clinical assessments (IGA, SD Severity Score)
- Record adverse events

* If subject meets all entry criteria at Screening, he/she can complete Baseline Visit on the same day (identical procedures do not need to be repeated). If more than 28 days has lapsed between screening and Baseline/Visit 2, then all procedures should be repeated except for re-obtaining informed consent. If subject has used a topical medication, then Baseline/Visit 2 will occur only after a 1 week washout period.

Visit 2 – Baseline (Week 0)

- Confirm all inclusion and exclusion criteria have been met
- Record concomitant medications and adverse events
- DLQI questionnaire
- Standardized clinical photography (including photographs of subject's entire face and close up photographs of the following facial regions: 1. Left cheek, 2. Right cheek, 3. Forehead and glabella)
- SD clinical assessments (IGA, SD Severity Score)
- Urine pregnancy test for all female subjects of child-bearing potential

- Collect blood samples for CBC with differential, Comprehensive metabolic panel (CMP), and C-reactive protein (CRP)
- Collect blood sample for possible future mechanistic analyses
- Urinalysis
- Perform tape strips of lesional and non-lesional skin. Lesional skin tape strips will be taken from area of worst clinical involvement
- Dispense/administer study drug

Visit 3 – Week 2

- Record concomitant medications and adverse events
- DLQI questionnaire
- SD clinical assessments (IGA, SD Severity Score)
- Urine pregnancy test for all female subjects of child-bearing potential
- Perform tape strips of lesional skin. Lesional skin tape strips will be taken from the same location as the lesional tape strips taken at Baseline.
- Dispense study drug and assess compliance. Subjects will report each study drug application, with 4 missed doses from Baseline considered non-compliance.

Visit 4 – Week 4

- Record concomitant medications and adverse events
- DLQI questionnaire
- Standardized clinical photography (including photographs of subject's entire face and close up photographs of the following facial regions: 1. Left cheek, 2. Right cheek, 3. Forehead and glabella)

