RNA-sequencing data will be profiled by Illumina NovaSeq 6000. RNA-sequencing data will be pre-processed using standard quality control metrics, such as FastQC and MultiQC, sequence alignment by STAR RNA-sequencing aligner and sequencing reads assignment to genomic features by featureCounts, followed by *voom*-transform. Mixed effect models will be used on R's limma framework and p-values for the moderated t-tests and paired-t-test will be adjusted by Benjamini-Hochberg procedure. Extensive bioinformatics tools will be employed to gain insights into the results. This will include (but will not be limited to) pathway and gene-set enrichment analyses by R package GSVA (Gene Set Variation Analysis) and by eXploring Genomic Relations (XGR) that uses prior biological knowledge and relationships from public databases.

We will perform proteomic biomarker studies in serum using the OLINK high-throughput proteomic platform, with the Explore panel that evaluates >1,500 protein analytes. Protein expression data will be modeled using a MMRM approach, with the interaction of study group (treatment /control) and timepoint as fixed effects and a random effect for each subject.

We will use the Spearman coefficient to correlate: 1) molecular markers with disease activity in SD at baseline; 2) changes from baseline in molecular markers with changes from baseline in IGA and overall clinical SD scoring at 4 weeks of treatment.

Data Transfer and Management

Data including the patient info, demographics, clinical scores and treatment allocation code will be sent to our Biostatistical Team in password-protected files.

Data from the [name] Lab (where all mechanistic studies will be done), including sequencing data and proteomics will be deposited in the Mount Sinai Box, which has the necessary safeguards for protection of human subjects research.

All data management steps taken to reformat and merge the clinical and laboratory data will be carried out using R codes, so all the steps of the processes can be reproduced.

Management of the Analysis

Analyses will be run in our desktops, with a backed-up copy in the Mount Sinai Box account. Once the analysis is finalized, all data will be deposited into the central file storage system (CFS), which is accessible to all research members. Both Mount Sinai Box and the CFS have backup capabilities and are encrypted and password protected.

Analysis of Safety and Tolerability

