Safety will be evaluated by tabulations of adverse events (AEs) and will be presented with descriptive statistics at each visit. AEs will be coded using the CTCAE, Common Terminology Criteria for Adverse Events, V 5.0. The number and percentage of subjects/lesions experiencing an AE/SAE will be stratified by system organ class, or a preferred term, and/or severity of the adverse event, and recorded and tabulated overall by each sub-strata. Each subject will be counted only once within a system organ class or a preferred term using the adverse events with the highest severity within each category. All information pertaining to adverse events noted during the study will be listed by subject, detailing verbatim given by the investigator, preferred term, system organ class, date of onset, date of resolution, severity, and relationship to treatment. A tabulation of AEs will be provided by subject.

DLQI (Dermatology Life Quality Index)

The DLQI is a validated questionnaire consisting of 10 questions that has been used in many randomized controlled trials in dermatology (20, 21).

Scoring

The scoring of each question is as follows:

Very much	scored 3
A lot	scored 2
A little	scored 1
Not at all	scored 0
Not relevant	scored 0

Question unanswered	scored 0
---------------------	----------

The DLQI is calculated by summing the score of each question. The maximum score is 30 and minimum score is 0. Higher score represents a quality of life that is more impaired.

Definition of DLQI Scores

0-1 = no effect at all on patient's life

2-5 = small effect on patient's life

6-10 = moderate effect on patient's life

11-20 = very large effect on patient's life

21-30 = extremely large effect on patient's life

A change in DLQI score of at least 4 points is considered clinically important (22). Such change suggests that there has actually been a meaningful change in that patient's quality of life since the previous measurement of his/her DLQI scores.

Table 1. Schedule of Events

Visit Week	(Up to -28 Days before Baseline)	0	2	4	6	X	Control Subjects
Visit #	1	2	3	4	5	Early Termination	1
Visit Type	Screening	Baseline	Tx	Tx	F-up		Screening / Baseline
Informed Consent	X						X
Inclusion / Exclusion Criteria	X	X ³					X
Demographics and Medical Hx¹	X						X
Urine Pregnancy Test	X	X ³	X	X	X	X	X
CBC w/differential; CMP; Urinalysis		X		X		X	X
Blood Sample Stored for Future Analysis		X		X		X	X
CRP		X		X			X
SD Clinical Assessments (IGA, SD Severity Score)	X	X ³	X	X	X	X	

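### The analysis section commits to Olink in serum, while the rest of the protocol puts Olink on tape strips and only stores the blood; the serum model's group-by-time interaction cannot be estimated

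*Combined protocol and SAP*

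**What the plan says.** **Analysis of Mechanistic (Exploratory) Endpoints.** The proteomic paragraph reads "We will perform proteomic biomarker studies in serum using the OLINK high-throughput proteomic platform", names the Explore panel, and models the protein data by MMRM "with the interaction of study group (treatment /control) and timepoint as fixed effects", plus a random subject effect. Appendix 5 shows that Amendment #2 revised this paragraph, added study group to a time interaction that was already there, and left the specimen as serum. It is current text. Earlier in the same section, gene and protein expression data already have a mixed model with tissue type (non-lesional, lesional, healthy) by timepoint.

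**Endpoints.** The first mechanistic endpoint ties the transcriptomic and proteomic work to skin obtained by tape strip. None of the four mechanistic endpoints mentions serum.

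**Mechanistic Analyses.** "proteomic studies on tape strip samples will be performed using the Olink Explore panel". On blood: "Blood samples at baseline and at Week 4 will be collected and stored for potential future analysis".

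**Study Design Overview.** For SD subjects: "Additional blood samples will be collected and stored at baseline and at Week 4", with early termination replacing Week 4 if it comes first. For controls, at the single Baseline/Week 0 visit: "blood and urine sample collection for standard laboratory testing, and a blood sample for possible future mechanistic analyses".

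**Procedures, withdrawal sections and Table 1.** The SD Baseline, Week 4 and Early Termination lists and the control Baseline list all carry the item "Collect blood sample for possible future mechanistic analyses". Study Withdrawal and Discontinuation of Treatment and Withdrawal of Subjects describe the exit blood sample in similar terms. The Table 1 row is "Blood Sample Stored for Future Analysis", marked for SD at Week 0, Week 4 and early termination, and once for controls.

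**The concern.** There are two linked problems.

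**Specimen.** One sentence makes serum proteomics a firm part of the study. Every other place that describes the mechanistic blood treats its use as optional and later, and the design section places the same panel on skin. The text could mean that serum is a wrong word for tape strips, that serum is an additional assay, or that it is the intended use of the stored blood. At stake are the scope of a large assay and whether serum proteins count among the molecular markers in the planned Spearman correlations. If this is left open, specimen and model could be chosen after data have been seen.

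**Model.** A treatment/control-by-timepoint interaction normally means a difference in change between two groups followed over time. This trial has one treated group and healthy volunteers with no follow-up visit, so that quantity does not exist in the data.

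**Working it through.** The documents give no sample size or power figure for serum proteomics, so there is no stated figure to reproduce. The check compares the texts and then examines what the sampling schedule can estimate.

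**Step 1: specimen, side by side.**

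| Place | Olink specimen | Status of mechanistic blood |
|---|---|---|
| Endpoints | tape-strip skin (first mechanistic endpoint) | not mentioned |
| Mechanistic Analyses | tape strips | stored |
| Study Design Overview | not stated | SD stored; control for possible later use |
| Procedures, withdrawal sections, Table 1 | not stated | stored or for possible later use |
| Analysis of Mechanistic Endpoints | serum | assay stated as a commitment |

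No section reconciles the last row with the others.

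**Step 2: samples at stake.** Inputs are 25 SD patients and 20 controls (Study Design Overview) and 20% dropout (Sample Size Calculation), so 25 × 0.20 = 5 patients may leave early. Assume full enrolment and that 0 to 5 SD patients lack a second draw.
- Upper: 25 (SD Week 0) + 25 (SD second draw) + 20 (controls) = 70.
- Lower: 25 + 20 + 20 = 65.

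Because early-termination draws are scheduled, up to 5 of the second draws at the upper end could come from an early-termination visit instead of Week 4.

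**Step 3: rank of the serum model.** Write the cell mean as μ + α·SD + β·W4 + γ·(SD × W4), taking the second draw as Week 4.

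| Cell | Sampled? | (μ, α, β, γ) |
|---|---|---|
| Healthy, Week 0 | yes | (1, 0, 0, 0) |
| SD, Week 0 | yes | (1, 1, 0, 0) |
| SD, Week 4 | yes | (1, 1, 1, 1) |
| Healthy, Week 4 | no | (1, 0, 1, 0) |

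The three sampled rows have rank 3 for 4 parameters. The additive model (without γ) also has rank 3, so the interaction contributes 3 − 3 = 0 of 1 degrees of freedom. β and γ appear only as the sum β + γ.

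- Estimable: SD Week 0 − healthy Week 0 = α; SD Week 4 − SD Week 0 = β + γ; SD Week 4 − healthy Week 0 = α + β + γ.
- Not estimable: difference in change = γ; SD Week 4 − healthy Week 4 = α + γ.

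**Step 4: does the non-estimable term damage the other contrasts?** The projection matrix of the interaction design was compared with that of a single three-level factor (healthy Week 0, SD Week 0, SD Week 4). The largest absolute difference was 4e-17 at N = 70 and 6e-17 at N = 65, which is rounding error. The two designs span the same space, so the estimable contrasts take the same values under either.

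**Step 5: would changing serum to tape strips be enough?** No. At Week 0 the SD group supplies lesional and non-lesional strips (25 + 25 = 50 at full enrolment); for the planned Week 4 analysis it supplies lesional strips only (up to 25). A two-level group factor puts all 50 baseline strips in one cell, so its Week 4 minus Week 0 contrast sets lesional skin against a mixture of both tissues. The same protein data would also have two models, because the tissue-type model already covers them.

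**The case against.** **The interaction costs nothing that was planned.** By Step 4 the useful contrasts survive, and software will usually drop the aliased term. This stands. A reader might infer that the serum results are invalid or that the plan claims a controlled treatment effect over time. The documents support neither. Mechanistic Analyses limits the healthy subjects to a baseline comparison, and no section states a difference in change against controls as an aim. What remains is a model statement naming a term the schedule cannot supply, with control left undefined.

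**Serum may be a deliberate extra assay.** Three of the four mechanistic endpoints name no specimen, Amendment #2 kept the word, and the blood needed is already scheduled. This also stands: it would be wrong to call the sentence a definite slip, or the assay definitely out of scope. But a firm commitment and storage for possible use cannot both describe the plan.

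**The skin model has the same gap.** A reader might extend the criticism to the tissue-type-by-timepoint model, since non-lesional and healthy skin are sampled only at Week 0. That extension does not hold as a defect: recoding would change no estimate, both baseline tissue contrasts are in the model, and so is the lesional Week 4 change.

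**It is only exploratory.** Agreed; this limits the weight of the point but does not resolve the contradiction.

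**Conclusion.** The point holds as a contradiction in current text plus a mis-stated model term. The documents do not settle whether Olink Explore in serum is part of this study. If it is, the interaction has 0 of 1 estimable degrees of freedom (3 of 4 cells, rank 3 of 4), and no controlled comparison of change is available. SD baseline versus healthy and SD Week 4 versus SD baseline are estimable and unaffected. The primary IGA analysis and the clinical secondary analyses are untouched.

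The rank result rests only on the sampling schedule: mechanistic blood at Week 0 and a second draw for SD patients, and once for controls. It does not depend on the sample counts. The figure of 65 to 70 samples assumes full enrolment and 0 to 5 missing second draws. The point should be settled before the proteomic analysis. It is more than clerical because it decides the scope of an assay, and because a one-word correction would pool lesional and non-lesional skin at baseline.

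**What to change.** Reconcile Endpoints, Study Design Overview, Mechanistic Analyses, the visit lists, the two withdrawal sections, Table 1 and the proteomic paragraph before any proteomic analysis. Choose one route.

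- **(a) No serum assay in this study.** Delete the serum model, or correct the specimen to tape strips and refer to the tissue-type model as the only protein model.
- **(b) Serum assay confirmed.** Replace the storage-only wording wherever it occurs and add serum to the mechanistic endpoints. In the model:
  - replace the interaction with one factor for the sampled cells (SD Week 0, SD Week 4, healthy Week 0), keeping the random subject effect;
  - define control as healthy volunteers at baseline;
  - state how early-termination draws are handled, and do not code them as Week 4 by default;
  - report Week 4 versus Week 0 as an uncontrolled within-patient change.

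The cost is protocol wording and model code, with no new samples or visits. Route (b) also confirms the expense of the serum assay; route (a) removes it.

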Appendix 1. Clinical Assessments

SD Severity Score

Clinical Feature	Score^a
Scale	0-4
Erythema	0-4
Pruritus	0-4
Total Score	0-12

^a0-4 for each clinical feature (0 = absence, 1 = mild, 2 = moderate, 3 = significant, 4 = severe)

Investigator Global Assessment

Clinical severity	Scored	Features
Clear	0	No signs of SD
Almost Clear	1	Just perceptible erythema and just perceptible scaling
Mild	2	Mild erythema and mild scaling
Moderate	3	Moderate erythema and moderate scaling
Severe	4	Severe erythema and severe scaling

Appendix 2.

Dermatology Life Quality Index

The aim of this questionnaire is to measure how much your skin problem has affected your life OVER THE LAST WEEK. Please check one box for each question.

1.	Over the last week, how itchy, sore, painful or stinging has your skin been?	Very much A lot A little Not at all	   	
2.	Over the last week, how embarrassed or self conscious have you been because of your skin?	Very much A lot A little Not at all	   	
3.	Over the last week, how much has your skin interfered with you going shopping or looking after your home or yard ?	Very much A lot A little Not at all	   	Not relevant 
4.	Over the last week, how much has your skin influenced the clothes you wear?	Very much A lot A little Not at all	   	Not relevant 
5.	Over the last week, how much has your skin affected any social or leisure activities?	Very much A lot A little Not at all	   	Not relevant 
6.	Over the last week, how much has your skin made it difficult for you to do any sport ?	Very much A lot A little Not at all	   	Not relevant 
7.	Over the last week, has your skin prevented you from working or studying ?	yes no	 	Not relevant 
	If "No", over the last week how much has your skin been a problem at work or studying ?	A lot A little Not at all	  	

8.	Over the last week, how much has your skin created problems with your partner or any of your close friends or relatives ?	Very much A lot A little Not at all	   	Not relevant 
9.	Over the last week, how much has your skin caused any sexual difficulties ?	Very much A lot A little Not at all	   	Not relevant 
10.	Over the last week, how much of a problem has the treatment for your skin been, for example by making your home messy, or by taking up time?	Very much A lot A little Not at all	   	Not relevant 

Appendix 3 CYP3A4 Inhibitors.

CYP3A4 Inhibitors

Amiodarone	Indinavir
Amprenavir	Isavuconazole
Aprepitant	Itraconazole
Atazanavir	Ketoconazole
Boceprevir	Lopinavir
Casopitant	Mibepradil
Cimetidine	Mifepristone (RU486)
Ciprofloxacin	Nefazodone
Clarithromycin	Nelfinavir
Cobicistat	Netupitant
Conivaptan	Nilotinib
Crizotinib	Norfloxacin
Cyclosporine	Norfluoxetine
Danoprevir	Posaconazole
Darunavir	Ritonavir
Delavirdine	Saquinavir
Diltiazem	Schisandra sphenanthera
Dronedarone	Telaprevir
Elvitegravir	Telithromycin
Erythromycin	Tipranavir
Faldaprevir	Tofisopam
Fluconazole	Troleandomycin
Gestodene	Verapamil
Grapefruit Juice, marmalade	Viekira pak
Idelalisib	Voriconazole
Imatinib	

Appendix 4 – Study Drug Label

Department of Dermatology
[contact]

GCO#22-0672 Seborrheic Dermatitis and Treatment Response to
Ruxolitinib 1.5% Cream

Subject # _____ Subject Initials: _____ Date: _____

Ruxolitinib 1.5% Cream - Apply as directed by the study doctor

PI: [name] [contact].

Store at controlled room temperature, away from light and humidity.

Caution: New Drug--Limited by Federal (USA) law to investigational use.

Appendix 5. Amendment Details

Amendment #1 May 25, 2022

Page 1 – Title Page – Added Amendment #1: May 25, 2022; Revised Date of protocol in footer.

Page 2 Table of Contents – Revised Page numbers and added Subject Identification and Appendices 3, 4 and 5.

Page 7 Inclusion Criteria for SD Subjects – Removed SD Severity Score as a criterion and added inclusion criterion: “Subject has failed an adequate course of treatment with at least one available therapy (topical antifungals or low-potency topical corticosteroids).”

Page 8 Exclusion Criteria for SD Subjects – Added Exclusion criterion: “Concurrent use of strong CYP3A4 inhibitors within 7 days or 5 half-lives (whichever is longer). A list of CYP3A4 inhibiting medications can be found in Appendix 3.”

Page 14 Stopping Rules – Added the following stopping rules:

- If the following lab results are abnormal, participants will be retested in a window of 7-10 days and reassessed. If the test results remain abnormal, participants will be discontinued from the study:

Hematology

Absolute Neutrophil Count: <1000/mm³; <1.0 x10⁹/L

Hemoglobin: <8.0 g/dL; <4.96 mmol/L; <80 g/L

Hemoglobin drop ≥2 g/dL from baseline on two consecutive blood draws with associated symptoms; or hemoglobin drop ≥3 g/dL from baseline on two consecutive blood draws without associated symptoms.

Platelet count: <75,000/mm³; <75.0x10⁹/L

Lymphocytes: <500/mm³; <0.5x10⁹/L

Chemistry

AST >3.0x ULN

ALT >3.0x ULN

Total bilirubin >1.5x ULN

CPK >10x ULN

Total bilirubin ≥1.5 x ULN; subjects with a history of Gilbert's syndrome may have a direct bilirubin measured and would be eligible for this study provided the direct bilirubin is ≤ ULN

- Other intercurrent illnesses or major surgery
- An infection that requires systemic treatment with antibiotic, antifungal, antiviral, anti-parasitic, or anti-protozoal agents or requires oral treatment with such agents for longer than 2 weeks
- Treatment with systemic corticosteroids or non-steroidal immunosuppressive/immunomodulating medications (e.g., cyclosporine, methotrexate, azathioprine, mycophenolate-mofetil, Janus kinase inhibitors, biologic agents, etc.).

Page 22 Appendix 1. Clinical Assessments – added a description of features associated with the individual scores of the Investigator Global Assessment.

Page 25 – Added Appendix 3 CYP3A4 Inhibitors

Page 26 – Added Appendix 4 Study Drug Label

Page 27 – Added Appendix 5 Amendment Details

Amendment #2 - October 24, 2022

Page 1 – Title Page – Added Amendment #2: October 24, 2022; Revised Date of protocol in footer.

Page 4 – Primary Endpoint

Revised from: “Percent of patients who achieve an IGA of 0 or 1 at 4 weeks of treatment with ruxolitinib 1.5% cream applied twice daily”

To: “The proportion of patients who achieve an IGA 0/1 at 4 weeks of treatment with ruxolitinib 1.5% cream applied twice daily”

Page 16 - Sample Size Calculation

Revised from: “30 moderate-to-severe patients treated with crisaborole for four weeks showed 67.8% average improvement in IGA with a standard deviation of approximately 50% (9). Assuming similar biological variation (sd = 50%), a sample size of n=20 SD patients provides 95% power at 5% significance to detect a minimum average improvement in IGA of 42.5% with the application of a two-sided paired t-test. Accounting for a 20% dropout rate, we, therefore, propose a sample size of n=25 patients.”

To: “A sample size of n=20 SD patients guarantees 90% power at 2.1% significance to detect a minimum proportion of 75% of patients with IGA 0/1 at week 4. This calculation assumes the application of the one-sided binomial test with a null hypothesis proportion of 40%. This proportion is based on the vehicle response benchmark reported by Zirwas et al.(2021) when comparing IGA 0/1 at week 8 in 154 patients treated with roflumilast foam 0.3% vs. 72 patients in the vehicle-controlled group(18). Accounting for a 20% dropout rate, we, therefore, propose a sample size of n=25 patients. “

Page 16 - Analysis of Primary Endpoint

Revised from “A Mixed-effects ordinal logistic regression model will be used to test differences in IGA between time points with time (Weeks 0, 2, 4, and 6) as a fixed effect, a random intercept for subjects, and inclusion of baseline characteristics as covariates. “

To: “The one-sided binomial test will be used to verify the hypothesis that the proportion of patients achieving IGA 0/1 at 4 weeks of treatment with ruxolitinib 1.5% cream applied twice daily is greater than 0.4.

Page 16 – Analysis of Secondary Endpoints

Revised from: “The mixed-effects model for continuous outcomes will also be used to detect any overall changes in clinical SD scoring over time compared with baseline with time (Weeks 0, 2, 4, and 6) as a fixed effect, a random intercept for subjects, and potential covariates. Changes in each component of the SD Severity Score, will also be evaluated using the same approach.”

To: “The two-sided Wilcoxon signed-rank test will assess the significance of changes from baseline in:

- IGA score at 4 weeks of treatment
- Components of clinical SD scoring (scale, erythema, and pruritus) at 4 weeks of treatment.

The two-sided paired t-test will assess the significance of changes from baseline in:

- Overall clinical SD scoring at 4 and 6 weeks of treatment.
- Vital signs measured in interval or ratio scale
- Analytes measured in interval or ratio scale from laboratory tests (hematology, serum, chemistry, and urinalysis) at 4 weeks of treatment

The p-values will be adjusted by the Bonferroni method. The frequency, duration, and severity of AEs will be summarized with tables and summary statistics.”

Page 17 - Analysis of Mechanistic (Exploratory) Endpoints

Revised from: “The baseline immune and molecular cutaneous profile of SD at baseline compared with healthy controls and the change in the immune and molecular cutaneous profile of SD with treatment will be assessed by MMRM approach. Gene/Protein expression data will be modeled using a mixed effect model with tissue type and time as a fixed effect and a random effect for each subject.”

To: “The baseline immune and molecular cutaneous profile of SD at baseline compared with healthy controls and the change in the immune and molecular cutaneous profile of SD with treatment will be assessed by MMRM approach. Gene/Protein expression data will be modeled using a mixed effect model with the interaction between tissue type (non-lesional/ lesional / healthy) and timepoint as fixed effects and a random effect for each subject.”

Revised from: “We will perform proteomic biomarker studies in serum using the OLINK high-throughput proteomic platform, with the Explore panel that evaluates >1,500 protein analytes. Protein expression data will be modeled using a MMRM approach, with time interaction as a fixed effect and a random effect for each subject.”

To: “We will perform proteomic biomarker studies in serum using the OLINK high-throughput proteomic platform, with the Explore panel that evaluates >1,500 protein analytes. Protein expression data will be modeled using a MMRM approach, with the interaction of study group (treatment /control) and timepoint as fixed effects and a random effect for each subject.

We will use the Spearman coefficient to correlate: 1) molecular markers with disease activity in SD at baseline; 2) changes from baseline in molecular markers with changes from baseline in IGA and overall clinical SD scoring at 4 weeks of treatment.”
